# 7.6 Post Randomization Participant Management

#### Clinical management

- A summary of the research management algorithm for patients in each of the two study groups will be strategically posted at clinic locations and will be placed in each participant's medical record; the patient should have an informational copy of their labs and management algorithm and advised to bring to scheduled and unscheduled visits.
- OB Welch Clinical labs staff will be available to draw labs at 4 and 8 weeks after initiation of therapy: if a patient has Clinical labs that are indicated for any other reason by primary OB, the study labs can be paired with the clinical draw.
- IV iron group will receive additional follow up for adverse symptoms 1 week post infusion and 4 and 8 weeks after initiation of treatment
- Oral iron group will receive survey of symptoms 1, 4, and 8 weeks after initiation of treatment
- Routine pregnancy care at each center will be given to patients by clinical providers trained in the study protocol.
- Ultrasound for anatomy or fluid/growth and antenatal testing will be per clinical center's routine.

# 7.7 Participant follow up

A clinic visit (preferred method) or follow up call will occur at 6 (4-12 weeks) weeks after delivery in accordance with routine postpartum care. Several data forms will be used during this follow-up process using forms for maternal outcomes, newborn outcomes, NICU outcomes, and 6 weeks follow up forms. These forms, HIPAA compliant, will be entered into the REDCap database.

At randomization, 24-28 weeks (up to 30 complete weeks if necessary) 4 and 8 weeks post-initiation (Oral iron)/ post-treatment (IV iron) labs will be collected as described above. We will also perform chart abstraction to determine hemoglobin levels at the time of admission for delivery and 1 day postpartum (these labs are drawn routinely at LPCH).

In addition to routine prenatal and postpartum clinic visits, participants will be followed up to ascertain maternal and infant status related to re/admissions and ER or unscheduled visits. The records of any ER visits or hospitalizations will be obtained for review.

# 7.8 Study Drug, Dispensing

Stanford's investigational pharmacy will dispense IV iron infusion to CTRU. CTRU will dispense/administer study infusion(s) to research participant and will provide oral acetaminophen prior to the initiation of IV iron infusion.

Participants receive medication supplies from the outpatient pharmacy. Oral iron tablets will be distributed 100 tablets at a time. Medication dispensing may occur in the intervening periods between visits in case of emergency, loss, or schedule changes. A tracking mechanism is maintained for all dispensing actions.

The participant will report by monitoring survey how many doses were missed. The only reasons that a patient may return the bottle include expired medication or if she does not tolerate the medication and is switched to something else. If the participant doesn't have enough left to supply her until her next visit, she will be dispensed a new bottle and told to complete the current supply and then start the new bottle

# 7.9 Biospecimens

7.9.1 Maternal Blood Samples will be collected at the following time points (see table below):

- Randomization (at 24-28 weeks age gestational age-optimal) may collect up to 32 weeks
- 4 weeks after post –initiation for oral group or post-completion for intravenous group.
- 8 weeks after treatment post –initiation for oral group or post-completion for intravenous group.
- Delivery\*
- Postpartum day 1\*

\* collected with routine delivery at LPCH. Routine CBC at birth admission and postpartum day 1 with LPCH. This will be in the patient's electronic health record.

#### 8. DELIVERY (including pregnancy loss after randomization) AND POST-DELIVERY

Outcome Data Collection and Chart Review Delivery Outcomes will be ascertained - on an ongoing basis until discharge.

Study personnel will abstract the hospital charts and compete information for REDCap entry:

- Labor and Delivery Data
- Neonatal Outcome Data
- Placental Pathology (review only if sent by primary Obstetrician)
- NICU admission form (if indicated)
- Adverse Event
- Study Intervention Discontinuation and Participation discontinuation/withdrawal

# 9. PROCEDURES FOR INACTIVE/ LOST/ REFUSED PARTICIPANTS AND MISSED VISITS

#### 9.1 Overview

Staff will use a systematic approach in attempting to recover reluctant participants, i.e., those who have either expressed interest in dropping out of the study or appear to be likely to drop-out due to noncompliance with any aspect of the study.

The goals to avoid drop-out and accomplish drop-out recovery include the following:

- 1. to ensure that participants are not pushed to the point that they refuse to participate further
- 2. to continue to engage participants through some form of contact (e.g., phone, e-mail) and allow an opportunity to determine participants' concerns and problem-solve for solutions to concerns and barriers to participation,
- 3. to foster some form of continued participation (e.g., even an agreement to allow future contact)

The general approach to drop-out recovery will involve contact by the study coordinator in an attempt to:

- 1. identify barriers to participation
- 2. problem-solve for solutions to overcome identified barriers
- 3. apply motivational enhancement methods

In situations where a participant's behavior suggests that she **does not** wish to participate, the participant can be removed from the study.

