#### Intravenous iron:

For adverse effects such as hypotension (maternal BP<90/60) and persistent dizziness, headaches, lightheadedness or fatigue and no other potential cause other than the medication, will be assessed for adverse reactions and any signs of anaphylaxis. Methylprednisolone, solumedrol, or dexamethasone, albuterol nebulizers, and intramuscular epinephrine will be available on site for any immediate concerns.

PLEASE REFER TO THE DETAILED ALGORTIHM APPROACH FOR MANAGEMENT OF ADVERSE REACTIONS: this is a figure from Rampton, et a "Hypersensitivity reactions to intravenous iron: guidance for risk minimization and management."

For patients that are stable for transfer, the plan will be for obstetric monitoring and further evaluation at the LPCH OB triage on the third floor. The location is across the street from the CTRU and Stanford/LPCH clinic. The patients will still be followed by the study in intent to treat fashion. In the cases of an unstable patient, 911 will be called and patient will be transferred immediately to the emergency room.

To increase effective management of possible hypersensitivity reactions in the IV group: the following have been included.

- Reference range of normal vitals in pregnancy
- Algorithm for management of hypersensitivity reactions

[figure not shown]

Figure 1. Algorithm outlining grading and management of acute hypersensitivity reactions to intravenous iron infusions. Details are given in the text.

- I. Management of mild Hypersensitivity reactions
- II. Mild of Moderate Hypersensitivity reactions
- III. Severe/life threatening Hypersensitivity reactions

Note: Methyl prednisone prior to IV infusion may considered on case by case basis for patients with history of asthma or high risk medication allergy.

Visit Description	Screening/ Enrollment	Treatment		4 weeks	8 weeks	Delivery	1 day	6 weeks
		IV Ferumoxytol	Oral Ferrous sulfate	Post-initiation/ Post- completion	Post-initiation/ Post- completion		Postpartum	postpartum
Visit Window	24-34 weeks GA	24-34 weeks	24-34 weeks GA up to delivery	•	•		1 day after delivery	
Screening of pregnant women with eligible hemoglobin and ferritin levels	X		•					
Review eligibility criteria	X							
Informed consent	X							
Iron studies with or without baseline complete metabolic panel (depending on history of liver or kidney disease)	X							
Randomization	X							
Assign study number	X							
Demographics	X							
Medical and obstetric history review	X							

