#### 9.2 Definition of Participant Status.

For purposes of the study, we define the following terms related to trial participation status:

- Active status active if iron medication therapy is managed according to the study algorithm. There may be instances where a provider is managing the participant's medications in accordance with the study protocol (i.e. many may commonly prescribe oral iron for anemia without iron studies), but the participant is obtaining medications from a (non-study) pharmacy of his/her choosing; in such situations, the participant is considered to be active as well.
- Inactive status –inactive or non-compliant if her iron medication is no longer being managed according to the study protocol with CTRU and she has not withdrawn consent for regular measurement (follow-up) visits or event monitoring is still being performed.
- Lost status —lost-to-follow-up if she has missed several appointments and cannot be contacted by any ordinary means (e.g., home phone, cell phone, mail, email, fax, etc.), clinic staff does not know the participant's whereabouts, and alternative contacts either do not know where the participant is or cannot be contacted themselves.

· Withdrawn/Refused status –participant is considered to be withdrawn if he/she has withdrawn consent to participate in the study and refuses further contact for any reason.

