# 12.3 Analyses

We will conduct an intent-to-treat analysis to compare the primary and secondary outcomes between the treatment arms. The primary outcome is the mean change in hemoglobin in oral vs IV iron over 4 weeks as well mean change in hemoglobin pre delivery. The primary outcome will be assessed using t-tests. Baseline characteristics between the groups will be compared using t-tests and chi-square tests. If there is an imbalance between the treatment arms, we will use multivariable regression modeling. Differences will be considered statistically significant at P<0.05.

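### Section 9.1 lets a randomized woman be removed without withdrawn consent, which conflicts with the status definitions in 9.2 and with the intent-to-treat analysis, and can bias the arm comparison

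*Combined protocol and SAP*

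**What the plan says.** Section 9.1 describes how staff try to keep reluctant participants. It covers women who say they may leave and those who "appear to be likely to drop-out due to noncompliance with any aspect of the study". After the retention goals and steps it closes with a removal rule: if a woman's behavior suggests she does not wish to take part, "the participant can be removed from the study". No criteria, decision-maker or time limit are given. The section does not say whether chart data are still collected afterwards.

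Section 9.2 defines participant status. A "participant is considered to be withdrawn if he/she has withdrawn consent to participate in the study and refuses further contact for any reason". A woman whose iron is no longer managed under the protocol is inactive, provided that "she has not withdrawn consent for regular measurement (follow-up) visits or event monitoring is still being performed".

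On analysis, Section 12.3 states: "We will conduct an intent-to-treat analysis to compare the primary and secondary outcomes between the treatment arms". The front summary also names intent to treat. Section 12.3 adds: "The primary outcome will be assessed using t-tests". It gives two primary measures, the change in hemoglobin over 4 weeks and the change before delivery, and no method for missing values.

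**The concern.** Removal under 9.1 happens after randomization, rests on an inference about the woman's wishes, and can be decided by someone who knows her arm, because Section 4.1 makes the trial open label. If removal ends data collection, her later hemoglobin values are missing, and a t-test on the available changes leaves her out. The two groups compared are then no longer the groups that were randomized.

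The opportunity for removal is not obviously the same in both arms. IV treatment is one or two supervised infusions. Oral treatment runs until delivery, with pill counts at 4 and 8 weeks. Reluctance may therefore show itself differently by arm. Section 3.2 also makes treatment discontinuation and adverse events secondary outcomes, and removal could leave those incompletely recorded.

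**Working it through.** **Setting the sections side by side**

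- 9.1: the trigger is behavior that suggests unwillingness, and the consequence is removal. Consent is not mentioned.
- 9.2: the trigger for withdrawn status is withdrawn consent plus refusal of contact. Non-compliance without withdrawn consent leads to inactive status. A woman removed on inferred unwillingness fits neither.
- 12.3 and the front summary: intent to treat, which needs outcomes on all randomized women or a stated way of handling those that are missing.
- 7.3, under intravenous iron, on women who have had a reaction: "The patients will still be followed by the study in intent to treat fashion". There is no matching sentence for women removed under 9.1.
- 5.7: a woman who refuses the records release is still followed if she agrees to contacts. 9.1 runs the other way.
- 7.9: "Routine CBC at birth admission and postpartum day 1 with LPCH". Section 7.7 takes the admission value from the chart, so removal can lose a primary value that needs no study visit.

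**How large a bias could be**

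The plan has no figure of its own for removal. The 20% drop-out allowance in Section 12.2 protects the number of women analyzed, not their comparability.

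Inputs from the documents: expected gains in Section 3.1 of 0.8 (IV) and 0.5 (oral) g/dL at 4 weeks, a difference of 0.3; 1.5 and 1.0 g/dL at birth admission, a difference of 0.5; 40 women per arm (Section 4.3).

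Assumed inputs, not in the documents: the share removed in each arm, r, and the gap g by which removed women's mean change falls below that of retained women.

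If m is the retained mean, the full-arm mean is (1 - r) × m + r × (m - g) = m - r × g. The retained mean is therefore too high by r × g, and

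bias in IV minus oral = r_IV × g_IV - r_oral × g_oral,

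which is g × (r_IV - r_oral) when the gap is the same in both arms.

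| Oral removed | IV removed | Gap, g/dL | Bias, g/dL | Size against 0.3 | Size against 0.5 |
|---|---|---|---|---|---|
| 5% | 0% | 0.3 | 0.3 × (0 - 0.05) = -0.015 | 5% | 3% |
| 20% | 0% | 1.0 | 1.0 × (0 - 0.20) = -0.20 | 67% | 40% |
| 20% | 5% | 0.5 | 0.5 × (0.05 - 0.20) = -0.075 | 25% | 15% |
| 5% | 20% | 0.5 | 0.5 × (0.20 - 0.05) = +0.075 | 25% | 15% |
| 10% | 10% | 0.5 in both | 0.5 × (0.10 - 0.10) = 0 | 0% | 0% |
| 10% | 10% | IV 0.3, oral 1.0 | 0.10 × 0.3 - 0.10 × 1.0 = -0.07 | 23% | 14% |

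At 40 per arm, 5% to 20% is 2 to 8 women. The last row shows that equal removal is not enough: the gaps must match too. Section 12.1 gives a between-arm difference of 1.5 g/dL instead; against that, the range -0.015 to -0.20 is 1% to 13%.

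**The case against.** The strongest reply is that 9.1 is loose drafting and the rest of the plan shows the right intent. Intent to treat is stated twice, IV women with reactions stay in follow-up, and Section 8 has staff abstract delivery data and record participation discontinuation. This stands in part: the intent is visible. But none of these passages says that data collection continues for a woman removed under 9.1.

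Four stronger readings are tempting, and the documents do not support them.

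- *Removed women are dropped from the analysis, so intent to treat is broken.* 9.1 does not say so. What can be said is that the rule conflicts with the stated analysis and permits loss of outcomes.
- *Non-compliance is grounds for removal.* In 9.1 it prompts recovery efforts. Removal has a different trigger, and 9.2 makes a non-compliant woman inactive.
- *Removal will fall on the oral arm's poorest responders, because about half of patients stop oral iron.* That figure, in Section 2.2, is background on stopping tablets, not on leaving a study. Women who do not tolerate oral iron are referred to discuss alternatives and may be considered for IV iron (Sections 7.2 and 7.3), so some may gain hemoglobin. Infusion visits could also put women off. A calculation that removes 20% of the oral arm with no gain, and nobody from the IV arm, gives a retained oral mean of 1.0/0.8 = 1.25 and cuts the 0.5 difference to 0.25. It assumes a gap of 1.25 g/dL and zero IV removal, neither of which is in the documents.
- *Everything lost can be recovered from the chart.* This holds for the routine birth-admission value. The 4-week CBC is scheduled as a study draw, paired with a clinical draw only when one happens to be due (Section 7.6).

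**Conclusion.** The point holds as a conflict between stated rules. 9.1 permits removal without withdrawn consent, 9.2 has no status for it, and it is at odds with the intent-to-treat analysis. Under t-tests with no missing-data method, nothing in the plan would correct the resulting loss.

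Bias is possible, not certain. It requires removal to differ by arm or to relate differently to outcome by arm. With oral removal of 5% to 20%, no IV removal and a gap of 0.3 to 1.0 g/dL, it is about -0.015 to -0.20 g/dL and understates the IV advantage. Heavier IV removal turns the sign, and equal removal with equal gaps gives zero. These rates and gaps are illustrations; the documents supply neither.

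**What to change.** Replace the removal sentence in 9.1 with text such as:

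> A woman whose behavior suggests that she no longer wishes to take part, but who has not withdrawn consent, is classed as inactive under Section 9.2. Study contacts may stop. Her birth-admission hemoglobin, delivery and safety data continue to be abstracted from the medical record within the consent she gave. Only a documented withdrawal of consent ends data collection. All randomized women are analyzed in the arm to which they were assigned.

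Extend the inactive definition in 9.2 so that it plainly covers this case.

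In 12.3, prespecify how missing 4-week values are handled, since the study draw may still be missed. One option is a mixed model for the repeated hemoglobin measurements, with a sensitivity analysis that shifts missing values in each arm separately, for example by 0 to -1.0 g/dL. Report losses by arm and reason.

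The cost is one replaced sentence, a small addition to 9.2, a short paragraph in 12.3, and slightly more abstraction and analysis work. No visits are added.

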#### 9.2 Definition of Participant Status.

For purposes of the study, we define the following terms related to trial participation status:

- Active status active if iron medication therapy is managed according to the study algorithm. There may be instances where a provider is managing the participant's medications in accordance with the study protocol (i.e. many may commonly prescribe oral iron for anemia without iron studies), but the participant is obtaining medications from a (non-study) pharmacy of his/her choosing; in such situations, the participant is considered to be active as well.
- Inactive status –inactive or non-compliant if her iron medication is no longer being managed according to the study protocol with CTRU and she has not withdrawn consent for regular measurement (follow-up) visits or event monitoring is still being performed.
- Lost status —lost-to-follow-up if she has missed several appointments and cannot be contacted by any ordinary means (e.g., home phone, cell phone, mail, email, fax, etc.), clinic staff does not know the participant's whereabouts, and alternative contacts either do not know where the participant is or cannot be contacted themselves.

· Withdrawn/Refused status –participant is considered to be withdrawn if he/she has withdrawn consent to participate in the study and refuses further contact for any reason.

#### 10. ADVERSE EVENT REPORTING

Serious adverse events that meet any of the following criteria:

- fatal or life-threatening
- result in significant or persistent disability,
- require or prolong hospitalization,
- result in a congenital anomaly/birth defect, or
- are important medical events that investigators judge to represent significant hazards or harm to research participants.

Specifically, any AE that meets any of these criteria (maternal death, ICU admission stroke, myocardial infarction, cardiomyopathy, fetal death or neonatal death) will be documented and reported as a SAE.

In addition, any unexpected event/ unanticipated problems which the investigator identifies will be reported.

# 10.1 Data Safety Monitoring Board

A DSMB will be activated to ensure the safety of participants by analyzing data and to oversee the validity and integrity of the data.

Any serious adverse event or unanticipated problem will be reported to the Stanford IRB. A Data Safety Monitoring Board (DSMB) will be established, with responsibility to monitor all aspects of the study and monitor data and oversee participant safety. DSMB participants include the senior faculty, staff, and representatives from the Stanford Maternal Fetal Medicine Division, Internal Medicine, Hematology and Nephrology. The DSMB will meet once a year to monitor safety, to advise on study progress and performance, protocol modification, or whether there should be early termination.

The outcome of reviews will be relayed to the IRB and protocol director.

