# **Timetable:**

Recruitment: 0-9 months
Data Collection: 0-12 months
Complete follow up: 0-16 months

Final data/primary analysis: 12-16 months

Sample size: 80

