- l. All newborn outcomes will also be ascertained through 6 (4-12) weeks through medical records chart review. If unscheduled visits occurred at another facility, obtain medical records release (if one has not already been obtained) to order hospital visit records.
- m. Data collection forms for maternal outcomes, newborn outcomes, NICU outcomes, and postpartum clinic/hospital outcomes will be completed by study personnel. These forms will be used to enter the clinical data into the study data base.

The Study Coordinator will be responsible for the day-to-day operations of the study at the clinical center, including recruitment and data collection processes. This responsibility includes the following:

- a. Establishing a method of training and monitoring to ensure primary obstetric providers are following the study treatment protocol during the pregnancy.
- b. Establishing a method to ensure that all potential participants receive medications and appropriate follow up
- c. Establishing a method that for screening women with IDA who are potentially eligible for the study e.g. dedicated clinic days or sessions.
- d. Assures that study drug is available at all times by checking the available drug supply at least weekly. The current workflow is that Stanford's pharmacy will dispense medications with Stanford's CTRU.
- e. Meeting with Stanford Investigational Drug Pharmacist pharmacy and/or site CTRU if necessary, to understand center specific drug request procedures.
- f. Arranging for the ordering and storage of study supplies.
- g. Collecting maternal and neonatal information necessary to complete all study forms.
- h. Will abstract information related to primary and other key outcomes, and assure that the PI and IRB (if required by institution) is notified of any primary outcome events and adverse events.
- i. Training additional staff as needed in data collection, forms completion and data entry.
- j. Coordinating data entry, including controlling access to the REDCap and study unit as applicable, and assuring that required back-up security and confidentiality procedures are maintained.
- k. Organizing and maintaining records, including the protocol, data forms, reports and correspondence

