#### 4.5 Timeline

Aim 1 Milestones	Q1	Q2	Q3	Q4
Extramural funding application preparation and submission. Letter of intent submitted to PCORI February 4 th ; full applications due May 5 th .	X			
Patient screening and enrollment. Patients identified via CBC testing during the second trimester				
Randomization. Patients randomized to IV iron cohort or Oral iron cohort	X			
Intervention. IV iron cohort receives intravenous iron. Oral iron cohort prescribed ferrous sulfate tablets.		X	X	
Data Analysis and Manuscript Preparation and Submission.			X	X

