#### After randomization:

- Provide medication and instructions based on the treatment arm randomized to
- Provide the group algorithm to both patient and provider.

Once the participant is randomized, the treatment algorithms will be conspicuously placed in the patient's medical record (whether electronic or paper medical record is utilized) such that providers will be aware of treatment plan at all times.

In both groups, serial CBC follow up and survey for symptoms will be assessed. Baseline data consisting gestational age of pregnancy, body mass index, pre-pregnancy weight and other prenatal data including baseline BP at the randomization visit will be included. Patients will be assigned to treatment groups by a concealed randomization allocation sequence using REDCap.

The categories of patients randomized:

Patients consenting to the study will be randomized 1:1 to two treatment groups

Group 1: Patients randomized to the IV iron group will receive treatment as follows:

- Women with Hgb 9-10.9 g/dL will receive one dose of 510 mg IV ferumoxytol
- Women with Hg 7-8.9 d/dL will receive two doses of ferumoxytol 510 mg 3-8 days apart for a maximum of dose of 1020 mg (see **Figure 2**).
- Patients will receive 650mg of Tylenol prior to initiation of the infusion
- The ferumoxytol is administered as an infusion for approximately 15-30 minutes. Patients will receive the IV iron at Stanford's Clinical and Translational Research Unit (CTRU) outpatient clinics with vitals collected before infusion and monitoring for 30minutes after infusion. Alternatively, patients who are admitted to the antepartum unit may receive the infusion inpatient.

For the IV iron group, follow up labs will be performed at 4 and 8 weeks after completion of infusion/s;

Group 2: The standard of care oral iron group will be prescribed 1-2 ferrous sulfate 325 mg tablets to be taken by mouth **every other day** until delivery. Dosage will be as follows for standardization:

- one ferrous sulfate tablet every other day if Hg 9-10.9 g/dL, and
- two tablets once every other day if Hg 7-8.9 g/dL.
- Oral medications will be dispensed by the CTRU or by the Outpatient Investigational Pharmacy (final confirmation pending contracts)
- Follow up labs will be drawn for both groups. For the oral iron group, it will be drawn 4- and 8-weeks post initiation of treatment

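### A once-yearly DSMB with no date for its first meeting can first convene after all IV iron in a nine-month recruitment plan has been given

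*Combined protocol and SAP*

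**What the plan says.** Section 10.1 makes the DSMB responsible for monitoring data and participant safety. It asks the board to advise on protocol changes and on "whether there should be early termination". The only timing given is "The DSMB will meet once a year to monitor safety, to advise on study progress and performance". Section 1.1.1 places the board in the oversight structure and section 1.5.2 keeps the regulatory binder available to it, but neither sets a meeting date.

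The Timetable in the synopsis plans "Recruitment: 0-9 months", with data collection to month 12 and follow-up to month 16. Section 4.3 sets the target at 80 women, 40 per arm. In the IV arm, women in the higher haemoglobin band have a single infusion and those in the lower band have "two doses of ferumoxytol 510 mg 3-8 days apart" (section 6, After randomization). Oral treatment runs on; its window in the visit table is "24-34 weeks GA up to delivery".

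On reporting between meetings, section 10.1 says "Any serious adverse event or unanticipated problem will be reported to the Stanford IRB". Section 1.1.2 asks the coordinator to "assure that the PI and IRB (if required by institution) is notified of any primary outcome events and adverse events". No section says that these reports also go to the DSMB.

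**The concern.** The interval between board meetings is longer than the planned recruitment period, and each woman's IV treatment is over within days. A board that first meets a year after the start could advise on modifying or ending an exposure that has already finished. The IV drug carries a boxed warning for serious hypersensitivity, some of it fatal (section 2.3.2), and the protocol describes another trial of this drug in pregnancy as not yet complete. The DSMB is the only body the plan asks to advise on early termination, so the timing of its first look decides whether that advice can affect IV exposure.

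**Working it through.** The plan gives no figure to reproduce, so this is timeline arithmetic with 1 month = 30.44 days.

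**Inputs from the documents**
- Recruitment ends at month 9 (Timetable).
- 80 women, 40 per arm (section 4.3).
- Second infusion at most 8 days after the first (section 6).
- Entry from 24w0d (section 5.5) to 34w6d (section 5.4), a span of 76 days.

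**Assumptions**
- First DSMB meeting at month 12.
- Even accrual, 80/9 = 8.89 women per month.
- A wait of 0 to 28 days from randomisation to first infusion, with 76 days as the extreme.
- Birth at 40 weeks.

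**Last infusion = 9 + (wait + 8)/30.44**

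| Wait to first infusion | Calculation | Month |
|---|---|---|
| 0 days | 9 + 8/30.44 | 9.26 |
| 28 days | 9 + 36/30.44 | 10.18 |
| 76 days | 9 + 84/30.44 | 11.76 |

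Every case precedes month 12.

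**IV women not yet randomised at a first meeting in month t = 40 - 40t/9**
- t = 4.5: 40 - 20 = 20
- t = 6: 40 - 26.7 = 13.3
- t = 9 or later: 0

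**If recruitment takes R months, IV women not yet randomised at month 12 = 40 - 40 × 12/R**
- R = 12: 0. Unfinished IV courses then number 40 × (8/30.44)/12 = 0.9 with no wait, and 40 × (36/30.44)/12 = 3.9 with a 28-day wait.
- R = 15: 8
- R = 18: 13.3

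**Oral arm at month 12.** The longest oral course is 16 weeks (24 to 40 weeks), or 112/30.44 = 3.68 months, so the last delivery is at 9 + 3.68 = 12.68.
- If all women enter at 24 weeks, those still on treatment number 40 × 0.68/9 = 3.0.
- If entry is spread evenly over 24w0d-34w6d (10.86 weeks), a woman entering at month 9 is still on treatment at month 12 only if her gestation at entry was below 26.95 weeks. The share is the triangle (0.68 × 2.95/2)/(9 × 10.86) = 0.0103, or 0.4 of 40.

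**Scale of the hazard.** Section 2.3.2 puts serious hypersensitivity below 1%. The chance of at least one event among 40 is 1 - (1 - p)^40: 3.9% at p = 0.1%, 18.2% at 0.5% and 33.1% at 1% (rates assumed within that bound).

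The milestone table in section 4.5 marks the row "Intervention. IV iron cohort receives intravenous iron. Oral iron cohort prescribed ferrous sulfate tablets" in the second and third quarters only. That agrees with dosing ending by about month 9. It is weak support, because randomisation is marked in the first quarter only and the enrolment row shows no mark as extracted. The conclusion does not depend on it.

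**The case against.** The strongest point is that month 12 is assumed. A meeting at month 5 or 6 would also satisfy a yearly rule. Section 1.1.1 gives the oversight structure tasks that belong before and during recruitment, which fits poorly with a board idle for a year. This stands: the wording permits a late first review but does not force one. A safeguard should still not depend on a date nobody has written down.

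Second, acute reactions are handled at the infusion itself. The plan has vital signs beforehand, at least 30 minutes of observation, a reaction algorithm (sections 2.3.2, 6.2 and 7.3), symptom follow-up (7.6) and named reporting of anaphylaxis (10.2), and serious events go to the IRB. All true, and it lowers the stakes. None of it is a board review of accumulating data by arm.

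Third, an early look is unlikely to show a rare reaction. With 20 IV women treated, the chance of at least one serious reaction is 1 - 0.99^20 = 18% at 1% and 1 - 0.995^20 = 10% at 0.5%. This also stands. The look would serve commoner adverse events and the general conduct of dosing as much as the boxed hazard.

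Fourth, recruitment may slip; section 13 foresees low enrolment. The gap then partly closes, but at 15 to 18 months' recruitment 32 to about 27 of the 40 IV women would still be randomised before a month-12 meeting.

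Last, the board draws partly on the division running the trial, and section 1.1.1 ties it to the committee that decides on analysis, while section 1.1.2 plans blinded outcome review. Interim results by arm would reach that group. This is a reason to confine the report to safety data, not to delay the review.

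**Conclusion.** The concern holds, at the strength of a possibility. As written, the plan allows all 40 IV courses to finish before the DSMB first meets. On a nine-month recruitment and a month-12 meeting, this is true for every wait to first infusion that the entry window allows. The result rests on the assumed meeting date and on recruitment keeping to schedule. With immediate infusion and the full 8-day gap, recruitment would have to run past about month 11.7 (12 - 8/30.44) before any IV course was left unfinished at month 12.

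The gap is confined to board review during IV dosing. Individual serious events still reach the IRB, a few oral participants may still be on treatment, and delivery and postpartum outcomes can be reviewed later. It does not affect the efficacy analysis. It should be corrected because the remedy is cheap and the present wording leaves the board's advice on IV exposure to chance.

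**What to change.** In section 10.1, replace the bare yearly rule with at least one DSMB review tied to enrolment while recruitment is open, and yearly meetings after that. About 40 randomised would do as a trigger. The number is only an example; any point well before the last IV participant would serve. State also that serious adverse events judged related to study drug go to the DSMB for unscheduled review, alongside the existing report to the IRB.

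The cost is a change of wording, one or two short extra meetings of a board already planned, an interim safety table by arm and a reporting route. The trial is open label, so the table reveals no individual allocation that is now hidden. It does put accumulating comparative data before the board, so it should hold safety data only. Sample size, eligibility and dosing are unchanged.
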